11.2.2. Paravalvular and Central Regurgitations

Paravalvular and Central leaks severity will be classified in

- none/trace,
- mild and
- moderate/severe

(section 18.12) and will be analyzed based on data observed while the subject remains on study as well as data imputed using multiple imputation (MI) methodology for time points at which no value is observed.

Multiple imputation will be performed under the assumption of missing-at-random (MAR) and will be implemented in two steps:

- Leak severity variable (categorical) will be coded with binary dummy indicator variables for the inclusion in the imputation model.
- Imputation assuming MAR will be carried out to impute missing data based on a multivariate joint Gaussian imputation model using the Markov chain Monte Carlo (MCMC) method. A separate imputation model will be used for each treatment arm. The imputation models will include countries, surgical approach, gender, age, hemodynamic assessments at each time point from Baseline. The MCMC method will be used with multiple chains, 200 burn-in iterations, and a non-informative prior. In case of non-convergence or non-estimability issues, a single model will be considered with treatment arm added as explanatory variable to the model. In case of further non-convergence the "mild" and "moderate/severe" classes will be merged.

Imputed data will consist of 200 imputed datasets. The random seed number for partial imputation with the MCMC method will be 2401, and the random seed number for the sequential regression multiple imputation will be 4181982.

The 200 imputed datasets will be used to graphically represent the trend on Leak severity (paravalvular and central) during time from baseline to 5 years by treatment arm.

12. SECONDARY COST-EFFECTIVENESS ANALYSIS

12.1. SURGICAL TIMES

12.1.1. Testing strategy

As secondary analysis, Cross clamp and Extracorporeal circulation times will be analyzed in a superiority context. A one-sided superiority test will be conducted comparing the treatment and control group at discharge in order to reject the null hypothesis that PERCEVAL is not superior to Stented valve, according to the following hypotheses:

$$H_0: \mu_{\text{PERCEVAL}} \geq \mu_{\text{CONTROL}}$$

$$H_1: \mu_{\text{PERCEVAL}} < \mu_{\text{CONTROL}}$$

where μ_{PERCEVAL} and μ_{CONTROL} are the surgical times (Cross clamp and Extracorporeal circulation times) of PERCEVAL and Control groups, respectively. Since statistical significance is needed for both time endpoints for claiming superiority on surgical times, no adjustment of multiplicity is necessary.

12.1.2. Surgical time analysis

Two independent Analyses of Covariance (ANCOVA) will be conducted to assess differences between treatments (Perceval vs Control) on:

- Cross clamp time
- Extracorporeal circulation time

after controlling for the effects of prognostic baseline/perioperative patient characteristic covariates (countries, surgical approach, concomitant procedure, gender, age).

The F-test of significance will be used to assess superiority of Perceval compared to Control. The test will be one-tailed with the probability of rejecting the null hypothesis when it is true set at $p < 0.025$.

The assumptions of normality and homogeneity of variance for performing ANCOVA will be assessed:

- Normality will be assessed using the One-Sample Kolmogorov-Smirnov test;
- Homogeneity of variance (both groups have equal error variances) will be assessed using Levene's Test for the Equality of Error Variances

As the sample size is large, small departures from normality can be detected. Because small deviations from normality do not severely affect the validity of ANCOVA tests, other statistics and plots will be examined to make a final assessment of normality:

- the skewness and kurtosis measures

- the histogram of distribution
- the Q-Q plot

As sensitivity analyses, the same ANCOVA models will be run considering also:

- previous cardiovascular procedure performed
- Medical History/Patient Risk Factors

A stepwise selection method will be used, with an Entry and Stay Significance Levels set at 0.15.

As additional sensitivity analysis, a non-parametric Kruskal-Wallis test will be performed to test the equality of medians between the treatment groups.

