10.1.5 SECONDARY ANALYSIS

Each component of the MACCE composite endpoint will be analyzed as proportion of subjects event-free at one year and their 95% C.I. will be reported. In addition, the primary endpoint will be analyzed by means of time-to-event methods (see section 10.1.6) as secondary analysis. For the Cox regression model, the stratification factors (country and surgical approach) and pre-operative variables (including demographic, medical history, and concomitant procedures) will be taken into account. All data collected up to cutoff date will be used for the time-to-event analysis.

Surgical times and Normalized Consumption Index endpoints will be analyzed in a superiority context. A one-sided superiority test will be conducted comparing the treatment and control group at discharge using appropriate regression models to account for stratification factors.

The serious adverse events will be assessed using descriptive statistics. Number of events and number of patients with at least one event will be presented in each group broken down by AE type. Number of events, as well as number and percentage of patients will be tabulated by timing (before / on or after intervention according to VARC-2 definitions). In case of some adverse events occur before intervention, they will be listed separately.

Number of events, as well as number and percentage of patients with at least one event will be reported overall and by treatment group in the Enrolled population, ITT population and Safety population.

Analysis on the secondary endpoint (section 8.5.8) will be detailed and defined in the Statistical Analysis Plan.

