Table 7 Overall operating characteristics

True MACCE _{ctrl}	True MACCE _{PERCEVAL}	True Effect	Pr(success)	E[N]
0.88	0.83	-0.05	0.025	1228.7
	0.88	0.00	0.704	1148.9
0.91	0.86	-0.05	0.023	1228.8
	0.91	0.00	0.805	1128.7

The level of significance of tests performed on secondary endpoints will be set at 0.05 two-sided.

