2.3. SAMPLE SIZE CALCULATION

Total sample size for this trial will be adaptively determined through interim analyses. The sample size will be approximately 900, 1050, or 1234 subjects.

The sample size is based on the analysis of primary endpoint (section 10.1) for assessing non-inferiority of Perceval valve arm compared to the control.

Based on CAVALIER experience, propensity score matched studies^{1,4,5,6} and, GARY registry⁷ the freedom from MACCE composite endpoint is expected to be similar for both arms. The original sample size of 1234 patients was based on CAVALIER experience which reported a freedom from MACCE at 1 year equal to 88%. Blinded review of the data for the ongoing current trial (database snapshot December 2017) estimated the pooled one year MACCE-free rate across arms at 91%, showing an overall primary endpoint higher than originally assumed. Due to this reason, 1234 patients may lead to an overpowered study and a smaller sample size may be required to demonstrate study objectives. In

order to adapt the sample size to the real study performance an adaptive design has been included in the study protocol.

Table 1 summarizes the overall operating characteristics of the design over a range of assumptions for the true underlying MACCE-free rate on control ($MACCE_{ctrl}$) and treatment ($MACCE_{PERCEVAL}$). The information provided by the table are:

- Pr(success): it is the proportion of simulated trials achieving success at the final analysis.
 - when the true effect is exactly at the non-inferiority margin (-0.05), it represents the Type I error; otherwise
 - Pr(success) is the power.
- E[N]: it represents the mean sample size across simulated trials, reflecting an average over some trials that stop with N = 900, some at N = 1050, and others at N = 1234.

Table 1 : Overall operating characteristics

True MACCE_{ctrl}	True MACCE_{PERCEVAL}	True Effect	Pr(success)	E[N]
0.88	0.83	-0.05	0.025	1228.7
	0.88	0.00	0.704	1148.9
0.91	0.86	-0.05	0.023	1228.8
	0.91	0.00	0.805	1128.7

Simulations indicate that the adaptive design is able to control the Type I error and Power of the study while looking for the most appropriate sample size. In fact, under the expected assumption of equivalent arms with 91% MACCE-free rate, the trial has approximately 80% power, the type I error rate is controlled to 2.5% one-side and the average sample size is reduced to approximately 1129.

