2.4. RANDOMIZATION

Subjects are randomly assigned in equal numbers (1:1) to one of two treatment arms:

- Perceval valve
- Standard sutured stented bioprosthetic aortic valve (control)

on the basis of a randomization list that has been performed before study start. Randomization list is stratified by 2 factors:

- country, and
- surgical approach (full sternotomy” or “mini-sternotomy”).

Only subjects who have undergone standard chest CT-scan to determine if the aortic stenosis can be replaced with an available Perceval valve, and is potentially suitable for mini-sternotomy, may be randomized. For each subject the randomization will be performed through eDC system after enrollment and before valve operation, specifically after CT scan and surgical approach (“full sternotomy” or “mini-sternotomy”) has been determined.

One patient will be considered adherent to the randomization if an attempt to implant of the allocated valve is performed. In case of, after an unsuccessful implant, a valve of the other arm is implanted the adherence to randomization allocation will be considered maintained.

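### SAP 12.1.2 attaches a one-tailed 0.025 superiority test on surgical times to a non-directional F-test and does not say how the one is obtained from the other

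*SAP*

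**What the plan says.** SAP 12.1.1 covers cross-clamp time and extracorporeal circulation time: "A one-sided superiority test will be conducted comparing the treatment and control group at discharge". The alternative hypothesis is that the Perceval mean is below the Control mean. Both times must succeed: "Since statistical significance is needed for both time endpoints for claiming superiority on surgical times, no adjustment of multiplicity is necessary".

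SAP 12.1.2 fits one ANCOVA per time, with treatment plus country, surgical approach, concomitant procedure, gender and age. It then gives the test in two sentences. The first is "The F-test of significance will be used to assess superiority of Perceval compared to Control". The second is "The test will be one-tailed with the probability of rejecting the null hypothesis when it is true set at" p < 0.025. The section does not say whether the F p-value is halved, whether the sign of the estimate must favour Perceval, or whether the adjusted difference and its confidence interval are reported.

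Protocol 10.1.5 agrees on sidedness: "A one-sided superiority test will be conducted comparing the treatment and control group at discharge using appropriate regression models to account for stratification factors". Protocol 10.2 sets the general level: "The level of significance of tests performed on secondary endpoints will be set at 0.05 two-sided". SAP 3.1 declares no change in the analysis from the protocol.

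**The concern.** The hypothesis has a direction and the named statistic does not. For a two-group factor, F is the square of t, so its single upper tail collects large differences both ways. Every ANCOVA F-test is upper-tailed in F, so a programmer can take the F p-value from the output, compare it with 0.025, and believe that the one-tailed instruction has been met. That rule is a two-sided t-test at 0.025, with only half of the error rate in the direction the hypothesis concerns. Another analyst, reading the one-tailed sentence as a statement about the treatment difference, would use the signed root of F and a different critical value.

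A prespecified superiority test should lead to one decision rule. Here the choice affects the critical value, the error rate and the power, and on one reading a check on the sign is missing. The rule is applied twice, because the claim needs both times to be significant.

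**Working it through.** **Inputs**
- Two arms, allocated 1:1 (SAP 2.4: "Subjects are randomly assigned in equal numbers (1:1) to one of two treatment arms"), so the treatment effect has 1 numerator df.
- Total N (SAP 2.3): "The sample size will be approximately 900, 1050, or 1234 subjects". The largest gives 617 per arm. Error df were taken as N − 2 and N − 30, to allow for covariates.
- Stated level: one-tailed 0.025 (SAP 12.1.2).
- Both times must be significant, so alpha is not split and no factor of 2 comes from multiplicity.

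**Step 1. Which rule reproduces the stated 0.025?** F(1, df) = t², so the F p-value equals the two-sided t p-value. At N = 1234, df = 1232:

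| Rule | Critical F | Critical \|t\| | Error rate |
|---|---|---|---|
| F p<0.025, no sign condition | 5.036 | 2.244 | 0.0250 over both directions |
| F p<0.025, counted only if Perceval is shorter | 5.036 | 2.244 | 0.0125 |
| F p<0.05 and Perceval shorter (signed root) | 3.849 | 1.962 | 0.0250 |

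The first row reproduces 0.025 only as a two-sided level. The third reproduces it as the one-tailed level of the stated hypothesis. Critical |t| for F p<0.025 stays between 2.244 and 2.245 for N = 900, 1050 and 1234 and either choice of df, so neither N nor the covariates matter. A simulation of 20,000 null trials with 617 per arm (unadjusted comparison, normal data) gave 0.023, 0.011 and 0.024 for the three rows.

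**Step 2. Relation to Protocol 10.2.** Two-sided 0.05 gives 0.05 / 2 = 0.025 in each direction. The signed-root rule matches this. The direct F p<0.025 rule gives 0.025 / 2 = 0.0125 and does not.

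**Step 3. Behaviour of the F statistic without a sign check.** With 617 per arm, F p<0.025 is reached with probability 0.31 if Perceval is truly slower by 0.1 SD, and 0.90 if slower by 0.2 SD. These are significant F values, not valid superiority findings. They show what a sign condition has to screen out.

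**Step 4. Power cost of the direct rule.** An effect with 80% power at one-sided 0.025 has Φ(0.842 + 1.960 − 2.241) = Φ(0.561) = 0.71 at 0.0125. With 617 per arm:
- difference of 0.15 SD: 0.75 at 0.025, 0.65 at 0.0125;
- difference of 0.20 SD: 0.94 at 0.025, 0.90 at 0.0125.

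Holding 80% power would need ((2.241 + 0.842) / (1.960 + 0.842))² = 1.21 times the sample size.

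**Step 5. Likely effect here.** Neither document gives a power calculation for surgical times. As a gauge only, the retrospective comparison of 65 and 65 patients cited in Protocol 6.3 gives:
- cross-clamp 58±26 against 26±10 min: pooled SD √((26² + 10²)/2) = 19.7, difference 32 / 19.7 = 1.6 SD;
- bypass 80±41 against 39±16 min: pooled SD √((41² + 16²)/2) = 31.1, difference 41 / 31.1 = 1.3 SD.

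For effects of this size, power at 0.0125 is about 1.0 for both times, even with 450 per arm.

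**The case against.** The strongest reply is that the SAP never says to compare the unhalved F p-value with 0.025. It states a one-tailed test with type I error 0.025, and the signed root of F delivers exactly that. The direction is set in 12.1.1, repeated in Protocol 10.1.5, and implied by the word superiority in 12.1.2, so no one following the hypotheses could call a slower Perceval result superior. One-sided 0.025 is also what two-sided 0.05 means in the favourable direction, so the stated level agrees with Protocol 10.2.

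Much of this stands. A reader might infer that the test really runs at one-sided 0.0125, that it has no direction at all, or that the SAP contradicts Protocol 10.2. The documents support none of these as a flat statement. The 0.0125 level and the mismatch with 10.2 follow only if the F p-value is compared directly with 0.025, and the hypotheses do carry a direction.

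The reply does not supply the missing step. Nothing in either document tells the analyst to halve the F p-value or to check the sign. Calling an F-test one-tailed does not settle it, because that phrase is true of every F-test in a sense unrelated to the direction of the treatment difference.

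**Conclusion.** The concern holds as an inconsistency between the named statistic and the hypothesis it is meant to test. SAP 12.1.2 allows two decision rules, with critical |t| of 1.96 or 2.24 and levels in Perceval's favour of 0.025 or 0.0125. Only the first matches the stated level and Protocol 10.2, and it is not written down.

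The consequence is small. The direct F p<0.025 rule is conservative, so false claims for Perceval are not inflated. If the true differences are anything like those cited in Protocol 6.3, both times would be significant under either rule. That rests on one retrospective study. For differences of 0.15 to 0.20 SD the choice would cost about 4 to 10 percentage points of power per endpoint at the full sample size. The error-rate results need only two arms and the usual ANCOVA assumptions.

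**What to change.** In SAP 12.1.2, replace the F-test sentence with a rule of this kind: for each of the two times, test the adjusted treatment difference (Perceval minus Control) from the ANCOVA with a one-sided t-test at 0.025, against the alternative that the difference is below 0. Equivalently, require the upper limit of the two-sided 95% confidence interval to be below 0. Report the adjusted difference and that interval for each time.

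This gives the error rate the SAP already states, carries the direction set in 12.1.1, fits Protocol 10.1.5 and 10.2, and follows the subtraction order in SAP 18.2. The model, covariates, data and the requirement that both times succeed stay as they are. The cost is one sentence in the SAP and the matching line of programming.

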12.2. NORMALIZED CONSUMPTION INDEX AND REDUCED NORMALIZED CONSUMPTION INDEX

12.2.1. Definitions

According to the CIP (Appendix 3), the Consumption Index (CI) will be define as the sum of all resources consumed, weighted for the contribution of unit cost of each event to the total cost:

$$CI = \sum_{j=1}^n \alpha_j E_j$$

where E_j is the observed value of event j and α_j is the ratio between unit cost of event j and the total cost. The Normalized Consumption Index will be define as a transformation of CI such that it ranges between 0 and 1. The simplest definition is

$$NCI = \frac{CI}{1 + CI}$$

The contributions of each event on the total cost (α_j) are reported in Table 5 and are calculated using result of 4 European countries (Italy, France, Germany, UK).

Table 5 : Contributions of each event on the total cost

Event (within discharge)	a_j	a*_j
OR time (hours – only first attempt)	0.1114	0.1177
Re-operation up to discharge (yes/no) [valve intervention within discharge]	0.2251	
ICU LOS (days)	0.0798	0.0843
Ward LOS (days)	0.0254	0.0268
Transfusion (units during implant and ICU)	0.0093	
Sepsis (yes/no) [from AE]	0.2544	
Was the subject under renal replacement (RRT) therapy in ICU? (yes/no)	0.0092	

Any Permanent Pacemaker Implant	0.2006	
Stroke (yes/no) [from AE]	0.2182	

Since OR time and hospital cost represent more than 95% of total cost for all countries, a reduced Normalized Consumption Index (rNCI) will be define as the previous index but using only OR time, ICU and ward length of stay ($\alpha * j$).

Descriptive analyses for NCI, rNCI, and their components will be reported overall, by treatment and stratified by country.

12.2.2. Testing strategy and analysis

As co-secondary analysis, Normalized consumption index and Reduced normalized consumption index will be analyzed in a superiority context. A one-sided superiority test will be conducted comparing the treatment and control group at discharge in order to reject the null hypothesis that PERCEVAL is not superior to Stented valve, according to the following hypotheses:

$$H_0: \mu_{\text{PERCEVAL}} \geq \mu_{\text{CONTROL}}$$

$$H_1: \mu_{\text{PERCEVAL}} < \mu_{\text{CONTROL}}$$

where μ_{PERCEVAL} and μ_{CONTROL} are the Normalized and Reduced normalized consumption indexes of PERCEVAL and Control groups, respectively. Since statistical significance is needed for both time endpoints for claiming superiority on consumption index, no adjustment of multiplicity is necessary.

If less than 5% of data for consumption indexes are missing, the analyses will be based on the complete cases and the comparison will be done by means of Wilcoxon-Mann-Whitney tests.

Otherwise, a multiple imputation process will be applied. In case of non-normality, data will be transformed toward normality before imputation using a logarithmic transformation. Treatment groups will be compared using Multiple Imputation (MI) approach and an ANCOVA model. Mean values of NCI and rNCI will be analyzed based on observed and imputed data. Multiple imputation will be performed under the assumption of missing-at-random (MAR) and will be implemented in using regression multiple imputation. The regression model will include as explanatory variables the treatment, surgical approach and the presence of concomitant procedures. No rounding or range restrictions will be applied. Imputed data will consist of 300 imputed datasets. The random seed number for the regression multiple imputation will be 9877. Each of the 300 imputed datasets will be analyzed by means of an ANCOVA analysis using the observed/imputed values as the dependent variable. The model will include as fixed effect categorical factors for treatment groups. Results from analysis of each imputed dataset, i.e., LSM treatment differences and their standard errors, will be combined using Rubin's imputation rules to produce a pooled LSM estimate of treatment difference, its 95% confidence interval, and a pooled p-value for the test of null hypothesis of no treatment effect.

In case of imputation, sensitivity analyses will be performed using complete cases and Wilcoxon-Mann-Whitney tests.

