8.5.7 RANDOMIZATION

Only subjects who have undergone standard chest CT-scan to determine if the aortic stenosis can be replaced with an available Perceval valve (size), and is potentially suitable for mini-sternotomy, may be randomized. For each subject the randomization will be performed based on the randomization list after enrollment and before valve operation, specifically after CT scan and surgical approach ("full sternotomy" or "mini-sternotomy") has been determined, to minimize bias.

Subjects will be randomly assigned in equal numbers (1:1) to one of two treatment arms. The blocked randomization list will be performed before the study start. The randomization will be stratified with 2 stratification factors, by country and by surgical approach (full sternotomy” or “mini-sternotomy”).

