10.6 PROCEDURES FOR REPORTING ANY DEVIATION(S) FROM THE ORIGINAL STATISTICAL PLAN

Any relevant change to the statistical analysis requested after protocol approval must be defined and approved through a protocol amendment or must be clearly mentioned in the statistical plan of the trial in a section 'Changes in the conduct of analyses from protocol', including the rationale of changes.

Deviations from the original statistical plan are unlikely. However, should they occur, they would have to be reported in the final study report.

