3. DOCUMENT AND CHANGE HISTORY

3.1.CHANGES IN ANALYSIS COMPARED TO CLINICAL INVESTIGATIONAL PLAN

No changes in the analysis as described in the Clinical Investigational Plan.

3.2.SAP AMENDMENT RATIONALE AND CHANGE HISTORY

Table 2 : SAP Amendment description

Version	Date	Section(s)	Description of modifications
1.0	13MAR2017		Initial Release.
2.0	26JUL2017	7,9,10,10,13	Additional general details on how to represent values in the statistical analysis. Additional specifications have been added to analysis populations (including the definition of adherence to randomization allocation). Details on compliance calculation have been added. Additional derivation rules.
3.0	28JUN2018	10, 11, 12 Editorial changes impact all the document	SAP has been amended following the CIP amendment: 
 Adaptive design; Primary analysis; Sensitivity analysis. Details on primary analysis (Bayesian approach) have been added. Additional analysis for NYHA, echocardiographic data, EQ5D. Surgical times analysis has been modified from ANOVA to ANCOVA. Editorial changes (new template per internal SOP). List of TFLs have been removed (included in a different document).
4.0	16MAY2019	12.1.2, 12.2, 12.3, 13.4	Sensitivity analyses of Surgical times have been added; Additional details for checking the assumptions for ANCOVA; Additional details have been added for the calculation and testing of NCI and rNCI, including the management of missing data (if needed) and an analysis by country; Sensitivity analyses of EQ-5D-5L have been added (using France-based scoring system and with a Mann-Whitney test); The use of a discount rate for the QALY has been removed; Additional details on calculation of EQ-VAS have been added; Details on pacemaker evaluation through ECG Core Lab have been added.

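### The SAP tests both consumption indexes without the stratification factors that the CIP requires, and declares no change

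*SAP*

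**What the plan says.** CIP section 10.1.5, repeated in the synopsis, puts surgical times and the Normalized Consumption Index endpoints in a superiority setting. It asks for a one-sided comparison of the arms at discharge "using appropriate regression models to account for stratification factors". Those factors are named in CIP section 8.5.7: "The randomization will be stratified with 2 stratification factors, by country and by surgical approach".

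SAP section 12.2.2 sets out the test of the index (NCI) and the reduced index (rNCI) in two branches:

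- With less than 5% of index data missing, "the analyses will be based on the complete cases and the comparison will be done by means of Wilcoxon-Mann-Whitney tests".
- Otherwise the index is multiply imputed and analysed by ANCOVA. On the imputation: "The regression model will include as explanatory variables the treatment, surgical approach and the presence of concomitant procedures". On the analysis: "The model will include as fixed effect categorical factors for treatment groups". The complete-case Wilcoxon-Mann-Whitney test then becomes the sensitivity analysis.

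Country is otherwise used for the indexes only in the descriptive summaries of SAP section 12.2.1.

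Surgical times fall under the same CIP sentence, and there SAP section 12.1.2 compares the arms "after controlling for the effects of prognostic baseline/perioperative patient characteristic covariates (countries, surgical approach, concomitant procedure, gender, age" (the list ends there).

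On departures from the CIP, SAP section 3.1 states: "No changes in the analysis as described in the Clinical Investigational Plan". CIP section 10.6 says that a relevant change to the analysis either goes through a protocol amendment or "must be clearly mentioned in the statistical plan of the trial in a section" on changes from the protocol, with its rationale.

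**The concern.** The SAP carries out the CIP instruction for one of the two endpoint groups it covers and drops it for the other without saying so. A reader who relies on SAP section 3.1 would think the index tests follow the CIP.

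The statistical cost is efficiency. Stratified randomisation removes between-stratum variation from the treatment comparison. A test that ignores the strata still counts that variation in its standard error, so the standard error is too wide. The test rejects less often than its nominal level under the null and less often than it could under a real effect.

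This matters because CIP section 3 names superiority in resource consumption at discharge as an aim of the trial, and SAP section 12.2.2 requires both indexes to be significant before it is claimed. The documents also give reason to expect that the strata predict the index. SAP section 12.1.2 treats country and approach as prognostic for surgical times. CIP section 6.3 argues that a minimally invasive approach shortens intensive-care and hospital stay, and both stays are index components.

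The 5% rule also moves the main comparison from ranks to means, although the hypotheses in SAP section 12.2.2 are written in terms of μ.

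**Working it through.** **Text comparison**

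| Item | Country | Surgical approach |
|---|---|---|
| Required in the test (CIP 10.1.5) | yes | yes |
| Surgical-time ANCOVA (SAP 12.1.2) | yes | yes |
| Index test, under 5% missing (SAP 12.2.2) | no | no |
| Index ANCOVA after imputation (SAP 12.2.2) | no | no |
| Index imputation model (SAP 12.2.2) | no | yes |

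Having surgical approach in the imputation model does not adjust the test.

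**Size of the effect (illustration)**

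The plan states no sample size or power for NCI or rNCI, so there is no figure to reproduce. Inputs:

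- One-sided level 0.025. SAP section 12.2.2 gives no level. CIP section 10.2 sets 0.05 two-sided for secondary endpoints, and SAP section 12.1.2 uses 0.025 one-tailed.
- R², the share of index variance explained by the strata: not in the documents, assumed 0 to 0.30.
- Power of the strata-adjusted test: not in the documents, assumed 80%, with 99% as an alternative.

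Under stratified 1:1 randomisation the treatment estimate has the adjusted variance, but the unadjusted standard error is larger by 1/√(1−R²). The unadjusted test therefore rejects only when the adjusted statistic exceeds 1.96/√(1−R²):

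- true one-sided level = 1 − Φ(1.96/√(1−R²))
- power = Φ(d − 1.96/√(1−R²)), with d = 1.96 + 0.842 = 2.802 for 80% adjusted power and d = 1.96 + 2.326 = 4.286 for 99%

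Worked case, R² = 0.30: 1.96/√0.70 = 2.343. The level is 1 − Φ(2.343) = 0.010. Power is Φ(2.802 − 2.343) = Φ(0.459) = 0.677.

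| R² | True one-sided level | Power if adjusted = 80% | Power if adjusted = 99% |
|---|---|---|---|
| 0 | 0.025 | 80.0% | 99.0% |
| 0.05 | 0.022 | 78.5% | 98.9% |
| 0.10 | 0.019 | 76.9% | 98.7% |
| 0.20 | 0.014 | 72.9% | 98.2% |
| 0.30 | 0.010 | 67.7% | 97.4% |

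**Simulation of the planned rank test**

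Assumptions: normal outcome, 1,110 patients, 12 countries by 2 approaches, permuted blocks of 4, effect scaled to 80% adjusted power, 4,000 replicates per R².

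| R² | Wilcoxon-Mann-Whitney | Van Elteren | Strata-adjusted ANCOVA |
|---|---|---|---|
| 0 | 78.2% | 77.5% | 79.6% |
| 0.05 | 76.8% | 77.8% | 80.6% |
| 0.10 | 75.2% | 77.6% | 80.1% |
| 0.20 | 69.2% | 76.3% | 78.9% |
| 0.30 | 65.6% | 77.6% | 80.5% |

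The gap between the two rank tests isolates the cost of ignoring the strata: 77.6 − 65.6 = 12.0 percentage points at R² = 0.30. The unstratified test's level there was 0.0105, against 0.010 from the formula.

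A second simulation applied the SAP transform CI/(1+CI) to a log-normal index (20 strata, 1,120 patients, 3,000 runs). The unadjusted rank test had 73.9% power against 79.4% for a strata-adjusted regression at R² = 0.10, and 65.1% against 79.9% at 0.30.

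**The case against.** The strongest case on the other side has four parts.

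- **Validity is not threatened.** A conservative test cannot manufacture a superiority claim, and the loss falls on the sponsor, on a secondary endpoint in a trial sized for its primary endpoint. This stands, and it is why the point concerns efficiency and agreement between documents.
- **The power loss is not anchored.** Neither R² nor the power for NCI is in the documents. At R² = 0.10, 90% adjusted power falls only to 88.0%, and 95% to 93.8%. This also stands: the figures illustrate a range, and the loss may be nil. The 1,110 patients simulated approximate 1234 less the 10% attrition to the Per Protocol population, whereas SAP Table 4 puts the cost-effectiveness analyses on the safety and mITT populations. Because the effect was rescaled to 80% power, this hardly changes the results.
- **Ranks may suit the data better.** With strong assumed skew (about 3.4), the unadjusted Wilcoxon test had 79%, 76%, 71% and 64% power at R² 0, 0.1, 0.2 and 0.3, against 65%, 67%, 67% and 63% for strata-adjusted ANCOVA on the untransformed scale. But the NCI is bounded between 0 and 1. When it was built by the SAP formula from assumed component distributions, skew was about 0.3. There the unadjusted Wilcoxon test fell from 22.6% to 16.7% power as R² rose to 0.19, while van Elteren and strata-adjusted ANCOVA held at about 23%. A preference for ranks is in any case met by a stratified rank test.
- **CIP section 10.1.5 leaves the detail of secondary analyses to the SAP.** That covers the choice of model. It does not extend to dropping the factors the same section says must be accounted for. The SAP sentence on fixed effects is loosely drafted, so treatment as the only term is its natural reading but not a certain one. The Wilcoxon branch has no such ambiguity.

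The version 4.0 entry in the SAP history mentions added detail on testing the indexes. It records a change between SAP versions and does not declare or justify a departure from the CIP.

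**Conclusion.** The concern holds. Both branches of SAP section 12.2.2 test NCI and rNCI without country or surgical approach, against CIP section 10.1.5, and SAP section 3.1 does not disclose it as CIP section 10.6 requires for a relevant change. The text conflict is certain, subject only to the loose wording of the imputation branch.

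The consequence is lost power and a test run below its nominal level, with no added false-positive risk. On an assumed 80% adjusted power and R² from 0.05 to 0.30, the loss is between 1.5 and 12.3 percentage points (80.0 − 78.5 and 80.0 − 67.7). It is at most 1.6 points if adjusted power is 99%, and zero if the strata do not predict the index. These figures are for a single index; no joint power for the two was computed.

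**What to change.** Amend SAP section 12.2.2 so that one prespecified strata-adjusted test, one-sided at 0.025, is primary for both indexes whatever the missingness:

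- **Preferred:** ANCOVA with treatment, country and surgical approach as randomised. Pool countries with fewer than 20 patients, as SAP section 11 already does. Fix the scale (log or untransformed) in the SAP now, so that it is not chosen after a look at normality. Run the model on complete cases when under 5% are missing and on the imputed datasets otherwise.
- **Acceptable alternative:** a van Elteren test stratified by the same factors, which also avoids dependence on the shape of the index.
- Add country to the imputation model.
- Keep the unstratified Wilcoxon-Mann-Whitney test as a sensitivity analysis.
- Adding concomitant procedure, as in SAP section 12.1.2, is optional.

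If the unadjusted test is kept instead, list it with its rationale in SAP section 3.1.

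The cost is SAP wording and two model terms. Both variables are already collected and already used in the surgical-time ANCOVA.
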